# C12. Incremental value of including air pollution in the PLCOm2012 lung cancer risk prediction tool to identify high-risk individuals for LDCT screening (Vancouver Site)

A detailed epidemiologic questionnaire (see appendix) will be administered to participants who consent to this optional study. The questionnaire is a modified version of the *Health and Lifestyle Core Questionnaire For Women and Men* (HLCQ) used in the Canadian Partnership for Tomorrow Projects (CPTP). This questionnaire is particularly thorough in collecting data on personal history and family history of cancer, smoking exposure, alcohol consumption and anthropometric measurement. These represent exposures that are active areas of lung cancer prediction research. For example, it is unclear how to optimally code family history of lung cancer in prediction models. Can prediction be improved by including number of family members with lung cancer (or other cancers) and should early age versus older age of onset be included? Personal history of cancer was an important predictor of lung cancer and PLCO analysis suggested that it might be a useful predictor in never-smokers. However, what components of personal history of cancer are important is unclear - which previous cancer types and which cancer treatment(s) are important are yet to be identified. Some of our recent analyses suggested

that very heavy alcohol use might be predictive of lung cancer independent of detailed adjustment for smoking exposure. But this exposure has not been included in any lung cancer risk prediction model to date. Body mass index has repeatedly been found to be inversely associated with lung cancer and has been included in several lung cancer risk prediction models, including all three PLCO models. However, the nature of the relationship is unknown, and if the underlying association can be more optimally measured for prediction is unknown. The PLCO cohort has 88% White, 5.2% Black, 1.9% Hispanic, 3.8% Asian, 0.6% Pacific Islander and 0.25% American Indian. Black race is a predictor in two of the U.S.-based PLCO models. The impact of race/ethnicity on lung cancer risk prediction in the BC population with different minority group is unknown. The proposed study will clarify these and additional relationships and help improve risk prediction.

A unique feature of this study is the ability to collect detailed residential history within Canada and prior residence outside of Canada (for foreign born immigrants) as well as household exposures from cooking and heating with solid fuels such as coal. From a full address, or just a city or street name – a coordinate value will be obtained from Google Maps (www.maps.google.ca) for each place of residence. The coordinates will be used for mapping of the long term air pollution exposure level (PM2.5) using satellite observations. We have previously developed global high resolution models of outdoor air pollution levels that have been successfully applied to epidemiologic analyses including cancer mortality in China and Canada. A time weighted air pollution exposure index will be developed from the intensity and duration of exposure similar to tobacco smoke exposure. We will also use our questionnaire to identify those who used solid fuels for cooking or heating and to generate exposure duration for household air pollution exposure. Since information on radon exposure based upon measurements from individual homes is usually lacking, we will test inclusion in the prediction model of estimated radon exposure based on risk prediction maps in a sensitivity analysis only.

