**Figure 7. Lung Nodule Management Protocol** 

## C2. Participant Inclusion and Exclusion Criteria

## C2.1 Inclusion Criteria

- Women or men age 55 to 80 years.
- Current or former smokers. A former smoker is defined as one who has stopped smoking for one or more years.
- An estimated 6-year lung cancer risk of ≥1.51% based on the PLCOm2012 risk prediction model
  or ≥ 30 pack-years smoking history (pack-year is defined as number of pack of cigarettes smoked per
  day multiply by the number of years smoked. If a participant stopped smoking for 6 months or more
  and then restarted smoking again, the time will be subtracted from the total duration of smoking in
  0.5-year increments)
- ECOG performance status 0 or 1.
- Capable of providing, informed consent for screening procedures (low dose spiral CT)

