C13.3 To determine the incremental value of air pollution for lung cancer risk assessment versus the PLCOm2012 model, newly diagnosed lung cancer patients (both ever-smokers and never-smokers) and the Lung Screening Study participants (ever-smokers) in the Vancouver site will be used to test if there is a significant difference in the pollution index between those with and without lung cancer and those who meet the PLCOm2012 6-year lung cancer risk threshold ≥0.0151 versus those who don't. We will externally validate any resultant risk prediction model using the Canadian Partnership for Tomorrow Project (CPTP) cohorts, the Canadian Communities Health Survey (CCHS) data linked to provincial cancer cancer incidence registries (Table 2), as well as the on-going 10,000 screening cohort from the National Taiwan University to determine the predictive performance (discrimination and calibration) of the model overall, and where numbers permit, in subsets and ethnic subgroups of the population. The CPTP and CCHS data linked to cancer registry outcomes provide ideal data for our efforts to validate the PLCO risk models and lung cancer screening selection criteria in Canadian settings, and to

potentially improve them. These data include prospective follow-up data which provide estimation of true risks based on incidence data (probability of lung cancer in a defined population at risk per defined time period).

We anticipate well over 1,700 lung cancers from the CPTP and CCHS cohorts. To minimize over-fitting of any new model, a rule of thumb suggests that 10-20 outcomes be present per predictor variable in the model. We expect all new models to have 15 or fewer predictors and thus do not expect serious problems with over-fit. We will also use bootstrap methods to estimate model *optimism*.

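### Section C12 describes the PM2.5 index by analogy with tobacco exposure; if it is cumulative it rises with age, and the C13.3 group comparisons, with no age adjustment stated, can be significant through age alone

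*Protocol*

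**What the plan says.** C12 derives PM2.5 at each place of residence from address coordinates: "The coordinates will be used for mapping of the long term air pollution exposure level". It then combines level and time: "A time weighted air pollution exposure index will be developed from the intensity and duration of exposure similar to tobacco smoke exposure". It gives no formula and no exposure window.

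The only tobacco measure in the protocol that combines intensity and duration is the pack-year in C2.1, which takes packs per day and says "day multiply by the number of years smoked". That is a cumulative product.

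C13.3 gives the purpose: "To determine the incremental value of air pollution for lung cancer risk assessment versus the PLCOm2012 model". The first analysis it names is to "test if there is a significant difference in the pollution index between those with and without lung cancer", and the second contrast is "those who meet the PLCOm2012 6-year lung cancer risk threshold ≥0.0151 versus those who don't". No age adjustment or matching is stated for either. C13.3 and the text after it then turn to a risk prediction model, with external validation, bootstrap optimism, AUC, NRI and calibration.

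**The concern.** The tobacco analogy does not carry over to outdoor air. Smoking starts and stops, so pack-years separate people of the same age. Everyone breathes outdoor air in every year of life, so over a lifetime history duration is close to age and a cumulative index is close to mean PM2.5 times age. As an illustration, two people who have always lived at 8 µg/m³ would score 8 × 60 = 480 at age 60 and 8 × 72 = 576 at age 72. That is a 20% difference (96/480) with identical air.

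Both C13.3 groupings may differ in age. C5.0 takes all newly diagnosed patients with no age limit, while screening participants must be 55 to 80 (C2.1). The threshold contrast is the more exposed, because A1 describes this kind of risk model as adding further factors to age and smoking history, so age helps to define the groups. At stake is a significant pollution difference that is really an age difference, read as support for adding pollution to the risk tool.

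**Working it through.** The protocol gives no effect size, PM2.5 spread, age gap or power for this comparison, so there is no stated figure to reproduce. The check asks how often a cumulative index would differ significantly when PM2.5 does not differ.

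**From the protocol**
- Patients: about 1,400 (C5.0).
- Vancouver screening participants: 2,000 (C3).
- Two-sided alpha: 0.05 (stated in C13.1, carried over to C13.3).
- Share at or above the PLCOm2012 threshold: 77.8% (C13.1), so 1,556 vs 444 of 2,000.

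**Assumed**
- Index = PM2.5 × age, with PM2.5 independent of age and of group.
- All 2,000 participants supply data.
- Mean age 65, age SD 6.
- CV of PM2.5 between people 0.15 to 1.0; age gap 0 to 7 years.

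**Formulae.** The mean PM2.5 level cancels, so the standardised difference is

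d = gap / √(SD² + CV² × (65² + SD²)), where SD is the age SD.

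The standard error of d is √(1/n₁ + 1/n₂) = √(1/1,400 + 1/2,000) = 0.0348. With t = d/SE, the rejection probability is Φ(t − 1.96) + Φ(−t − 1.96).

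**Worked example: gap 3 years, CV 0.3.** The denominator is √(36 + 0.09 × 4,261) = √419.5 = 20.48, so d = 3/20.48 = 0.1465, t = 4.20 and Φ(2.24) = 0.988. At CV 0.5 the denominator is √(36 + 0.25 × 4,261) = 33.19, so d = 0.0904, t = 2.59 and Φ(0.63) = 0.737.

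**Lung cancer vs none, 1,400 vs 2,000, cumulative index, no age adjustment**

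| CV of PM2.5 | no gap | 1 year | 2 years | 3 years | 5 years |
|---|---|---|---|---|---|
| 0.15 | 5% | 71% | 99.9% | 100% | 100% |
| 0.3 | 5% | 29% | 80% | 99% | 100% |
| 0.5 | 5% | 14% | 41% | 74% | 99% |
| 0.75 | 5% | 9% | 21% | 42% | 83% |
| 1.0 | 5% | 7% | 14% | 26% | 59% |

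At CV 1.0 and a 7-year gap the figure is 87%. An age SD of 9 changes little at CV 0.3 and above; at CV 0.15 and a 1-year gap it lowers 71% to 58%.

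**Above vs below the threshold, 1,556 vs 444, 5-year gap:** 100%, 99.5%, 80%, 47% and 29% for CV 0.15, 0.3, 0.5, 0.75 and 1.0.

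**Simulation check** (1,000 data sets per setting, lognormal PM2.5, mean age 63 plus the gap, age SD 7, Welch t test, 1,400 vs 2,000). The cumulative index without adjustment rejected in 78%, 42% and 13% of runs at a 2-year gap for CV 0.3, 0.5 and 1.0, and in 100%, 99% and 56% at a 5-year gap. A Mann-Whitney test gave the same picture. With a time-weighted average, or with the cumulative index adjusted for age, rejection was 4% to 6% at gaps of 0, 2 and 5 years.

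**The case against.** The strongest reply is that the protocol does not fix a cumulative index. C12 calls it time weighted, an average also uses intensity and duration, the pack-year definition sits in the eligibility criteria and is not cited in C12, and no lifetime window is stated. The definition and the covariates may be in a statistical analysis plan that is not shown. This stands in part: the wording is ambiguous, and the point applies only if the index is cumulative. It does not remove the point, because the protocol itself chooses the tobacco analogy, which points towards a cumulative measure, and itself names the group difference in pursuit of incremental value.

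A reader might infer that the fault lies in the index itself. It does not: the same cumulative index, adjusted for age, keeps its nominal error rate. The weakness is the combination of a cumulative index with a comparison that does not account for age.

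A reader might also infer that the sub-study cannot answer objective 2.1. The documents do not support that. The planned work includes a prediction model assessed by AUC and NRI, and if pollution is added to a model that already contains age, this mechanism does not operate there.

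Finally, the protocol gives neither an age gap nor a PM2.5 spread. Prior residence outside Canada, which C12 collects, would widen the spread and weaken the effect.

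**Conclusion.** The point holds in a conditional form. If the C12 index is cumulative, as its wording most naturally suggests, the C13.3 group comparisons can reach significance through age with no true PM2.5 difference. It would be too strong to say that an age gap will produce such a result. For the patient comparison the chance runs from about 7% (1-year gap, CV 1.0) to nearly 100% (gaps of a few years, CV 0.3 or less), and it is the nominal 5% with no gap. These figures rest on the assumed gaps and CVs, on lifetime exposure, and on PM2.5 levels unrelated to age. The matter deserves correction, but it is confined to an optional single-site sub-study and does not touch the primary objectives.

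**What to change.** In C12, define the PM2.5 index as the duration-weighted average concentration: the sum of intensity × years divided by the sum of years.

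In C13.3, state that any comparison using a cumulative index is adjusted for age or for the PLCOm2012 linear predictor. State also that incremental value is judged by the model that adds pollution to PLCOm2012, not by the raw group difference.

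A common look-back window is optional, for example as a sensitivity analysis. As a requirement it would be a trade-off, because it may discard earlier exposure, including the residence abroad that C12 sets out to capture.

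The cost is a few sentences and a little more analysis work. The residential and age data are already to be collected.

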# C13. Statistical Considerations

C13.1 In the PLCO intervention arm smokers, the mean PLCOm2012 estimated 6-year lung cancer risk was 3.9%. This suggests that in a similar sample of 4000 smokers screened and followed for six years, 155 lung cancers would be detected. Assuming that 85.3% and 77.8% of the samples will be positive by the USPSTF criteria and PLCOm2012 risk>1.51% criteria, respectively, and that the sensitivity to detect

lung cancer are 83.8% and 94.3%, respectively, our sample size of 4000 will have greater than 90% power to demonstrate that compared to the USPSTF criteria, the PLCOm2012 criteria selects a significantly smaller proportion of individuals and detects a significantly higher proportion of lung cancers. Our study will have a 39% power to demonstrate that the positive predictive power for PLCOm2012 (4.2%) is significantly greater than observed for the USPSTF (3.4%). The numbers used in these calculations come directly from PLCO data. A two-sided alpha error of 0.05 was applied. The correlation between the two criteria was -.222. Power calculations were performed using STATA MP 14.1 software (College Station, Texas) using bootstrap resampling methods and the *power pairedproportions* program based on McNemar's test.

C13.2 For screening CT detected lung nodules, the retrospective analysis by van Riel et al suggest the PanCan nodule management protocol may have better sensitivity and specificity than Lung-RADS . (Figure 3, 4). Each management schema has unique harms and benefits with possible costs differences so we will undertake a prospective comparison of the PanCan probabilistic strategy and the LungRADS nodule classification. Since the Lung-RADS also recommend using the PanCan nodule protocol for class 4 findings, a randomized trial comparing the two would not be meaningful. We will determine their effect on the frequency of additional imaging, biopsies, surgical resection, and outcomes of these procedures (diagnosis, False positives, False negatives). Through an iterative process, the management protocols will be evaluated every six months to determine if revision is warranted).

C13.3 To determine the incremental value of air pollution for lung cancer risk assessment versus the PLCOm2012 model, newly diagnosed lung cancer patients (both ever-smokers and never-smokers) and the Lung Screening Study participants (ever-smokers) in the Vancouver site will be used to test if there is a significant difference in the pollution index between those with and without lung cancer and those who meet the PLCOm2012 6-year lung cancer risk threshold ≥0.0151 versus those who don't. We will externally validate any resultant risk prediction model using the Canadian Partnership for Tomorrow Project (CPTP) cohorts, the Canadian Communities Health Survey (CCHS) data linked to provincial cancer cancer incidence registries (Table 2), as well as the on-going 10,000 screening cohort from the National Taiwan University to determine the predictive performance (discrimination and calibration) of the model overall, and where numbers permit, in subsets and ethnic subgroups of the population. The CPTP and CCHS data linked to cancer registry outcomes provide ideal data for our efforts to validate the PLCO risk models and lung cancer screening selection criteria in Canadian settings, and to

potentially improve them. These data include prospective follow-up data which provide estimation of true risks based on incidence data (probability of lung cancer in a defined population at risk per defined time period).

We anticipate well over 1,700 lung cancers from the CPTP and CCHS cohorts. To minimize over-fitting of any new model, a rule of thumb suggests that 10-20 outcomes be present per predictor variable in the model. We expect all new models to have 15 or fewer predictors and thus do not expect serious problems with over-fit. We will also use bootstrap methods to estimate model *optimism*.

If the PLCOm2012 model performs in the Canadian population as well as in the PLCO cohort (AUC 0.80), it may be difficult to find significant incremental improvement in AUC from the addition of new predictor(s) to the model. Net Reclassification Improvement (NRI) is a method that is more sensitive at identifying prediction improvements at important decision-making thresholds. The NRI has been criticized recently and as a response it has been recommended that the number of risk categories for decision-making be kept small and risk boundaries are clinically relevant. We will apply these guideline in our application of NRI.

The predictive performance of the PLCO models will be assessed by AUC, a measure of discrimination or ability to classify correctly, and assessing calibration (do model-estimated probabilities correspond to observed probabilities). Calibration will be evaluated graphically by plotting observed risk versus model-estimated risk by deciles of model risk. Calibration will also be evaluated by assessing the magnitude of the mean and 90th percentile absolute error (observed minus predicted risks), and by applying Cox recalibration (logistic recalibration). The efficiencies of the PLCOm2012 risk ≥0.0151 and the USPSTF criteria to select high risk smokers for LDCT screening will be compared by applying these criteria to the prospective data and determining the number that are criteria-positive, sensitivity, specificity and PPVs. Confidence intervals for proportions will be prepared using the exact binomial method. Statistical measures of performance fail to estimate clinical benefit of one method over another. We will apply *decision curve anaysis* to compare net benefit diferences between the diferent models and criteria.

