## **Project Summary**

Background. The cost-effectiveness of a population-based lung cancer screening program with low-dose computed tomography (LDCT) to reduce lung cancer mortality is strongly influenced by the sensitivity and specificity of the selection criteria for screening. Retrospective analysis by [name] and coworkers showed that the PLCOm2012 lung cancer risk prediction model using 7 non-smoking and 4 smoking variables detects 7.6% more lung cancer and samples 8.7% fewer people compared to the US Preventive Services Task Force (USPSTF) screening inclusion criteria based on age and smoking history alone. The sensitivity and specificity of PLCOm2012 versus USPSTF screening criteria to select smokers for lung cancer screening has not been prospectively evaluated in the general population.

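### C13.1's power of more than 90% holds for the proportion selected but not for sensitivity, where its own inputs give about 80% at 4,000 participants

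*Protocol*

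**What the plan says.** Section C13.1 gives one power statement for two results at N = 4,000. Its inputs are:

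- Cancers: "in a similar sample of 4000 smokers screened and followed for six years, 155 lung cancers would be detected". This is derived from a mean model-estimated six-year risk of 3.9%.
- Proportions selected: "Assuming that 85.3% and 77.8% of the samples will be positive by the USPSTF criteria and PLCOm2012 risk>1.51% criteria, respectively".
- Sensitivities, in the same order, for detecting "lung cancer are 83.8% and 94.3%, respectively".
- Correlation: "The correlation between the two criteria was -.222".
- Two-sided alpha of 0.05, with bootstrap resampling and a paired-proportions program based on McNemar's test.

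From these it concludes that "our sample size of 4000 will have greater than 90% power to demonstrate that compared to the USPSTF criteria", PLCOm2012 both selects a smaller proportion and detects a higher proportion of cancers. It separately gives 39% power for positive predictive values (PPVs) of 4.2% against 3.4%.

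**The concern.** The two halves of the claim rest on very different numbers. The proportion selected is compared in all 4,000 participants. Sensitivity is compared only in those who develop lung cancer, so its effective sample is about 155 pairs. A single figure for both hides this, and a 10.5-point difference in 155 pairs with negatively associated rules does not obviously reach 90%.

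Sensitivity is Aim 1 and the first half of hypothesis 1. If the true power at 4,000 is nearer 80%, the chance of missing the assumed difference in that cohort is about 20%, not under 10%. A non-significant result from Phase I alone could then be read as stronger evidence against PLCOm2012 than it is.

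**Working it through.** **Formula.** For paired proportions with discordant cells p10 and p01, d = |p01 − p10| and s = p10 + p01, McNemar power at two-sided 0.05 is Φ[(d√n − 1.96√s) / √(s − d²)].

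**1. What the correlation says about the whole sample.** If nobody is negative on both rules, the both-positive cell is 0.853 + 0.778 − 1 = 0.631. The correlation is then (0.631 − 0.853×0.778) / √(0.853×0.147×0.778×0.222) = −0.222, the stated value. So the stated margins and correlation imply an essentially empty negative-on-both cell: allowing for rounding, at most about one person in 4,000. This fits C4.2.2, which takes forward for screening those who meet either rule.

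**2. Proportion selected (reproduces).** p10 = 0.222, p01 = 0.147, d = 0.075, s = 0.369, n = 4,000. The formula gives Φ[(4.743 − 1.191)/0.603] = Φ(5.89), more than 99.9%.

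**3. PPV power (reproduces).** An unpaired test of 3.4% against 4.2%, with 0.853×4,000 = 3,412 and 0.778×4,000 = 3,112 positives, gives 39.5%. The plan says 39%.

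**4. Sensitivity (does not reproduce).** If the negative-on-both cell is empty in the whole sample, it is empty among the cancers. The discordant cells are then 1 − 0.838 = 0.162 and 1 − 0.943 = 0.057, so d = 0.105 and s = 0.219. The implied correlation among the cancers is (0.781 − 0.838×0.943) / √(0.838×0.162×0.943×0.057) = −0.108.

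At n = 155: Φ[(0.105×12.450 − 1.96×0.468)/0.456] = Φ(0.855) = 80.4%.

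| Test version, 155 cancers, empty cell | Power |
|---|---|
| Formula above | 80.4% |
| Score McNemar, enumerated | 82.3% |
| Continuity-corrected, enumerated | 76.6% |
| Exact, enumerated | 76.7% |

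If the one person allowed by rounding were a cancer (1/155 = 0.65%), the discordant cells would be 0.0505 and 0.1555, and the formula gives about 83%.

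**5. Other readings of the correlation at 155 cancers.**

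| Correlation among cancers | Formula | Score test |
|---|---|---|
| −0.222 (negative-on-both cell would be −1.0%, impossible) | 76.9% | 78.3% |
| 0 | 83.8% | 86.2% |
| +0.1 | 87.0% | 89.7% |
| +0.2 | 90.1% | 93.0% |

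An unpaired two-sided test gives 84.5%. A one-sided McNemar test with the empty cell gives 88.1%, but C13.1 fixes a two-sided alpha.

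**6. Cancers needed for 90%.** At n = 205 the formula gives Φ[(0.105×14.318 − 0.917)/0.456] = 90.1%. At 155 per 4,000, that is about 5,290 participants.

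**7. The cancer count.** The PPVs imply 0.042×0.778×4,000/0.943 = 138.6 and 0.034×0.853×4,000/0.838 = 138.4 cancers, a frequency of about 3.46% against the stated 3.9%. With 155 cancers the PPVs would be 155×0.943/3,112 = 4.7% and 155×0.838/3,412 = 3.8%. At n = 139 the formula gives Φ[(0.105×11.790 − 0.917)/0.456] = 75.9%.

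**8. All 8,000.** Doubling gives 277 cancers (from the PPVs) to 310 (from the stated count), with power of 96.6% to 97.9%.

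**The case against.** The strongest reply is that the shortfall concerns one cohort. Study Plan item 3.2 sets the prospective evaluation on 8,000 people, where power is about 97% to 98%. C5.0 adds an optional Vancouver series, estimated at 1,400 newly diagnosed patients, in which the same two rules are compared among ever-smokers. Both points stand. A reader might infer that Aim 1 as a whole is underpowered; the documents do not support that. But the power claim is made expressly for 4,000, and C3 makes the second 4,000 conditional on institutional approval.

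A reader might also infer that the stated correlation is wrong. It is not: −.222 is right for the whole sample, and C13.1 never says that it was applied to the cancers. A correlation of +0.222 would give 90.8%, so a lost minus sign is a possible explanation, but only a guess.

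The bootstrap cannot be rerun from the document. It might have used other data, but the published margins and correlation leave almost no room for a different cancer table.

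The count of 139 is an inference, not the plan's stated assumption. The 3.9% is a mean model-estimated risk, while the PPVs may be observed values. The cancer count could also be higher, since participants are to be followed for at least six years, but C13.1 relies on 155.

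Finally, the Project Summary says that PLCOm2012 "detects 7.6% more lung cancer and samples 8.7% fewer people", which might suggest a smaller effect than C13.1 assumes. That figure comes from a retrospective analysis and is not an input to C13.1, so it shows no error in the power.

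**Conclusion.** The statement of more than 90% power is correct for the proportion selected and wrong for sensitivity. On C13.1's own inputs, power for sensitivity at 4,000 participants is about 80%, within 77% to 82% across versions of McNemar's test. The chance of missing the assumed difference in that cohort is therefore about twice the implied maximum of 10%. None of the two-sided calculations with a zero or negative correlation among the cancers reaches 90%; the highest is 86%, by the score test at zero correlation.

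The result rests on 155 cancers, the stated sensitivities, and the empty negative-on-both cell that the stated margins and correlation imply. If the cancer frequency behind the PPVs is the right one, power is about 76%. This should be corrected, but it neither undermines the design nor shows that more participants than the planned 8,000 are needed.

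**What to change.** In C13.1:

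- Split the power claim. For the proportion selected, state more than 99%. For sensitivity at 4,000 participants with 155 cancers, state about 80%, naming the version of the test.
- Keep −.222 as the whole-sample correlation and add the value for the cancer table, about −0.108.
- Reconcile the cancer frequency (3.9% against about 3.46%). If the lower one is kept, state about 139 cancers and about 76%.
- Optionally, add that if Phase II is approved and all 8,000 are pooled (277 to 310 cancers), power would be about 97% to 98%. Whether the pooled cohort becomes the primary analysis set is a separate design choice that this correction does not require.

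The cost is a change of wording and one less favourable figure. No data collection or recruitment target changes.

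### The 39% power stated in C13.1 for PPV is not the power of a valid comparison of two PPVs in the same 4,000 people; a paired comparison has more than 99% under the plan's own assumptions

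*Protocol*

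**What the plan says.** Protocol C13.1 plans for 4,000 smokers followed for six years. It takes a mean six-year risk of 3.9% from the PLCO trial's intervention-arm smokers and concludes that "155 lung cancers would be detected".

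- **Shares selected:** "Assuming that 85.3% and 77.8% of the samples will be positive by the USPSTF criteria and PLCOm2012 risk>1.51% criteria, respectively".
- **Sensitivities to detect** "lung cancer are 83.8% and 94.3%, respectively" (USPSTF first).
- **Main claim:** "our sample size of 4000 will have greater than 90% power" to show that PLCOm2012 selects fewer people and detects more of the cancers.
- **PPV claim:** "Our study will have a 39% power to demonstrate that the positive predictive power for PLCOm2012 (4.2%) is significantly greater" than the 3.4% for USPSTF.
- **Error rate and dependence:** "A two-sided alpha error of 0.05 was applied", and "The correlation between the two criteria was -.222".

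The section attributes its power calculations as a whole to bootstrap resampling and to a Stata paired-proportions routine based on McNemar's test. It does not say which of these gave the 39%. The closing paragraphs of C13 say that PPVs, among other measures, will be determined and compared on the prospective data, with exact binomial intervals for proportions.

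**The concern.** PPV is one of three measures that Study Plan item 3.2 names for the prospective evaluation. The first outcome in C11, the number needed to screen to detect one cancer, is in essence its reciprocal. A stated power of 39% tells readers that the study probably cannot settle this question.

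That sits oddly with the rest of C13.1. The ratio of the two PPVs is the sensitivity ratio times the inverse ratio of the shares selected: (0.943/0.838) × (0.853/0.778) = 1.125 × 1.096 = 1.23, which matches 4.2/3.4. The section claims more than 90% power for each component and 39% for their product. The likely reason is that the 39% does not account properly for the large group selected by both criteria. That group contributes the same cancers to both PPVs and almost cancels from the difference.

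**Working it through.** **Inputs (all from C13.1).** N = 4,000; two-sided alpha 0.05; selected 85.3% (USPSTF, n = 3,412) and 77.8% (PLCOm2012, n = 3,112); sensitivities 83.8% and 94.3%; PPVs 3.4% and 4.2%; correlation -.222; 155 cancers.

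**1. Reproducing the 39%.**

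*Route A, independent samples.* Pooled p = (3112 × 0.042 + 3412 × 0.034)/6524 = 0.0378. The SE under the null is 0.00473 and under the alternative 0.00475. Power = Φ[(0.008 − 1.96 × 0.00473)/0.00475] = Φ(−0.267) = 39.5% (39.1% unpooled).

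*Route B, McNemar formula with PPVs as inputs.* Joint probability = 0.034 × 0.042 − 0.222 × √(0.034 × 0.966 × 0.042 × 0.958) = 0.00143 − 0.00807 = −0.0066. The discordant probabilities are then 0.0406 and 0.0486, sum 0.0893. Power = Φ[(0.008√4000 − 1.96√0.0893)/√(0.0893 − 0.008²)] = 39.5%.

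Route B is not admissible. A joint probability cannot be negative, and the lowest possible correlation for these margins is −0.00143/0.03635 = −0.039. It also borrows the correlation between selection criteria, and it ignores that the two PPVs have different denominators. Route A ignores the overlap. The two cannot be told apart from the printed figure.

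**2. Overlap.** Selected by both = 0.853 × 0.778 − 0.222 × √(0.853 × 0.147 × 0.778 × 0.222) = 0.6636 − 0.0327 = 0.631. This leaves 22.2% USPSTF only, 14.7% PLCOm2012 only and 0% neither: 2,524, 888, 588 and 0 people.

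**3. Cancers.** With no cancers outside both criteria, the share in both groups is 0.838 + 0.943 − 1 = 0.781. USPSTF only has 0.057 and PLCOm2012 only 0.162.

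**4. Cancer frequency.** Working back from the printed PPVs: 0.042 × 0.778/0.943 = 3.47% and 0.034 × 0.853/0.838 = 3.46%, or about 138 to 139 cancers. Working forward from 155: 0.943 × 155/3112 = 4.7% and 0.838 × 155/3412 = 3.8%.

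**5. Paired variance of the PPV difference.** Each person contributes [PLCOm2012 positive] × (D − 0.042)/3112 − [USPSTF positive] × (D − 0.034)/3412, where D = 1 for cancer. The squared contributions, summed at 138.5 cancers, are:

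| Group | People | Cancers | Variance contribution |
|---|---|---|---|
| Both | 2,524 | 108.2 | 0.10 × 10⁻⁶ |
| PLCOm2012 only | 588 | 22.4 | 2.23 × 10⁻⁶ |
| USPSTF only | 888 | 7.9 | 0.72 × 10⁻⁶ |
| Total | 4,000 | 138.5 | 3.05 × 10⁻⁶ |

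For example, the PLCOm2012-only term is 22.4 × (0.958/3112)² + 565.6 × (0.042/3112)² = 2.23 × 10⁻⁶. The SE is 0.00175, against 0.00475 under independence. Then z = 0.00795/0.00175 ≈ 4.6, and power = Φ(4.56 − 1.96) = 99.5%. At 155 cancers the difference is 0.0089, the SE 0.00184 and the power 99.8%.

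**6. Simulation.** Multinomial samples of 4,000 from these cells, tested with a score-type or Wald statistic that allows for the pairing, give about 99.8% power at 138.5 cancers and 99.9% at 155. Other admissible overlaps (selection 66% to 77%, cancers 78% to 83%) give at least 99.8%. With two-thirds of 138.5 cancers (about 92, roughly four years' worth), power is still about 98%.

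**The case against.** Four points can fairly be made for the protocol.

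- **The cause is not documented.** A reader might infer that the sponsor treated the groups as independent samples. The protocol does not support that as fact: it names a paired routine and a correlation, and Route B gives the same 39.5%. What stands is that neither route found gives a valid PPV power.
- **No unpaired PPV test is planned.** A reader might infer that a real PPV advantage would usually be reported as not significant. An unpaired test run on these overlapping data would indeed have only about 22% power (138.5 cancers) to 31% (155). But no section prescribes such a test, the only test the protocol names is paired, and the choice of PPV test may properly sit in the SAP.
- **PPV has not been abandoned.** A reader might take the 39% as writing PPV off. C13.1 only reports a figure, and the closing paragraphs of C13 still plan the comparison.
- **PPV does not carry the design.** Hypothesis 1 concerns cancers detected and the proportion selected; Aim 1 concerns sensitivity. If both parts of Hypothesis 1 hold in the one cohort, the PPV advantage follows algebraically. The error understates power, so it neither makes 4,000 too few nor biases any estimate.

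These points limit the cause, the consequence and the severity. They do not rescue the 39%.

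**Conclusion.** The point holds in this limited form. Under the plan's own margins, sensitivities and correlation, the stated 39% should be above 99%: about 99.8% at a cancer frequency of 3.46% and 99.9% at 3.9%. The protocol gives margins and one correlation, not the joint cells. The cancer split rests on there being no cancers outside both criteria, which follows because the stated correlation leaves nobody in that group; the result barely moves under other feasible overlaps. It also assumes the six-year cancer yield.

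The inconsistency between 155 cancers and the printed PPVs is a separate arithmetic fault in the same paragraph. It does not drive the power result, which is above 99% at either frequency.

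This should be fixed as a wrong stated power. Nothing in this point bears on the sample size or on the validity of the primary sensitivity comparison.

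**What to change.** In C13.1:

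1. Replace the 39% with the power of a paired PPV comparison, which is above 99% under the stated six-year assumptions, and give the joint cells used.
2. Say that the PPV comparison uses that paired method: a weighted generalised score test, a relative predictive value with robust variance, or a participant-level bootstrap. The detail can go in the SAP.
3. Use one cancer frequency throughout: either PPVs of 4.2% and 3.4% with about 138 cancers (3.46%), or 4.7% and 3.8% with 155.

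The cost is a wording change and one recalculation. The data, follow-up and number of participants stay the same.
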